11.1.2 Other significant adverse events (OAE)

During the evaluation of the AE data, an AstraZeneca medically qualified expert will review the list of AEs that were not reported as SAEs and discontinuation of IP due to AE (DAEs). Based on the expert's judgement, significant AEs of particular clinical importance may, after consultation with the Global Safety Physician, be considered OAEs and reported as such in the CSR. A similar review of laboratory/vital signs/ECG data will be performed for identification of OAEs.

Examples of these are marked haematological and other laboratory abnormalities, and certain events that lead to intervention (other than those already classified as serious), dose reduction or significant additional treatment.

11.2 Calculation or derivation of pharmacokinetic variables

The PK analyses of [¹⁴C] radioactivity concentration data in whole blood, plasma, urine, and faeces and AZD9291, AZ7550 and AZ5104 concentration data in plasma and urine will be performed at . Pharmacokinetic analyses will

be conducted according to Standard Operating Procedures unless otherwise specified.

Total [^{14}C] radioactivity in whole blood and plasma will be converted to concentration equivalents of AZD9291 based on the actual specific activity of the dose.

Pharmacokinetic parameters will be derived using noncompartmental methods with Phoenix[®] WinNonlin[®] version 6.3 or higher (Pharsight Corp., Mountain View, California, United States). All PK computations will be performed using Phoenix[®] WinNonlin[®] version 6.3 or higher or SAS[®] version 9.2 or higher (SAS Institute, Inc., Cary, North Carolina, United States). Graphics will be prepared with SAS version 9.2 or higher, SigmaPlot[®] version 12.3 or higher (Systat Software, Inc., San Jose, California, United States) or Phoenix[®] WinNonlin[®] version 6.3 or higher.

Actual elapsed time from dosing will be used for final blood and plasma based PK parameter calculations. Pharmacokinetic parameter units will be consistent with the concentration units specified in the bioanalytical data. For units with a mass element, both absolute weight (eg, ng) and molar weight (eg, nano mole) will be reported.

The following PK parameters will be determined for plasma AZD9291, AZ7550 and AZ5104 and whole blood and plasma [^{14}C] radioactivity:

AUC	Area under the concentration-time curve in the sampled matrix from time zero to infinity, calculated by linear up/log down trapezoidal summation
AUC _(0-t)	Area under the concentration-time curve in the sampled matrix from time zero to the time of the last quantifiable concentration, calculated by linear up/log down trapezoidal summation
AUC ₍₀₋₇₂₎	Area under the concentration-time curve in the sampled matrix from time zero to the time of 72 hours, calculated by linear up/log down trapezoidal summation
AUC ₍₀₋₂₄₎	Area under the concentration-time curve in the sampled matrix from time zero to the time of 24 hours, calculated by linear up/log down trapezoidal summation
C _{max}	Maximum concentration in the sampled matrix, obtained directly from the observed concentration versus time data
t _{max}	Time to C _{max}
t _{lag}	Lag time before observation of quantifiable analyte concentrations
CL/F	Apparent oral clearance (AZD9291 plasma, whole blood and plasma radioactivity only)

V_z/F	Apparent volume at distribution (AZD9291 plasma, whole blood and plasma radioactivity only)
$t_{1/2,\lambda_z}$	Elimination half-life
λ_z	Elimination rate constant
M/P_{AUC}	AUC metabolite to parent ratio, AZ7550 or AZ5104 AUC/AZD9291 AUC adjusted for differences in molecular weight (AZD929 =499.62; AZ5104 and AZ7550=485.59). If AUC is not reportable in most volunteers, $AUC_{(0-t)}$ will be used rather than AUC.
$M/P_{C_{max}}$	C_{max} metabolite to parent ratio, AZ7550 or AZ5104 C_{max} /AZD9291 C_{max} adjusted for differences in molecular weight (AZD9291=499.62; AZ5104 and AZ7550=485.59)
$C_{max}(PL)/C_{max}(PR)$	C_{max} ratio of plasma AZD9291, AZ7550 or AZ5104 (PL) to plasma radioactivity (PR)
$C_{max}(WBR)/C_{max}(PR)$	C_{max} ratio of whole blood radioactivity (WBR) to PR
$AUC(PL)/AUC(PR)$	AUC ratio of plasma AZD9291, AZ7550 or AZ5104 (PL) to plasma radioactivity (PR). If AUC is not reportable in most volunteers, $AUC_{(0-t)}$ will be used rather than AUC.
$AUC(WBR)/AUC(PR)$	AUC ratio of WBR to PR. If AUC is not reportable in most volunteers, $AUC_{(0-t)}$ will be used rather than AUC.

The following PK parameters for plasma AZD9291, AZ7550 and AZ5104 and whole blood and plasma [^{14}C] radioactivity will be calculated for diagnostic purposes and listed, but will not be summarised:

$t_{1/2}$, Interval	The time interval of the log-linear regress to determine $t_{1/2}$
N	Number of data points included in the log-linear regression analysis used to determine λ_z (a minimum of 3 data points will be used for λ_z determination)
Rsq	Coefficient of determination for calculation of λ_z (λ_z and related parameters will be reported only if Rsq is 0.800 or more)
%AUC _{ex}	Percentage of AUC obtained by extrapolation (if the extrapolated area is greater than 20% then AUC for that specific profile will not be reported)

The ratio of plasma AZD9291, AZ7550 and AZ5104 to plasma radioactivity concentrations, and whole blood to plasma [^{14}C] radioactivity concentrations and the distribution of

radioactivity in blood cells (expressed as percentage) will be reported for each sampling time to assess the radioactivity distribution in blood based matrices over time.

The distribution of radioactivity in red blood cells will be calculated by the following equation:

$$\frac{C_{wb} - (1 - Ht) \times C_p}{C_{wb}} \times 100\%$$

Where C_{wb} is concentration in whole blood, C_p is concentration in plasma and Ht is haematocrit (Ht will be the mean value of the laboratory Ht data obtained from Day -1, 7, 14, and 28).

The following PK parameters will be computed from the urine AZD9291, AZ7550, AZ5104, and urine total radioactivity:

Ae_u	Amount recovered in urine during each collection interval (t_1 to t_2), calculated as urine concentration or concentration equivalent x urine volume
Cum Ae_u	Cumulative amount recovered in urine
fe_u	Percent (or fraction) of actually administered dose/radioactivity recovered in urine during each collection interval and overall (AZD9291 and urine total radioactivity only)
Cum fe_u	Cumulative percent (or fraction) of actually administered dose/radioactivity recovered in urine (AZD9291 and urine total radioactivity only)
CL_R	Renal clearance calculated as $CumAe_u/AUC_{(0-t)}$ (AZD9291, AZ7550, and AZ5104 only)

The following parameters will be computed from the faecal total radioactivity versus time data:

Ae_f	Radioactive amount recovered in faeces during each collection interval (t_1 to t_2), calculated as [faecal radioactive concentration equivalent x faeces weight]
Cum Ae_f	Cumulative radioactive amount recovered in faeces
fe_f	Percent (or fraction) of actually administered radioactivity recovered in faeces during each collection interval and overall
Cum fe_f	Cumulative percent (or fraction) of actually administered radioactivity recovered in faeces

For all calculations, the faecal weights reported by the bioanalytical laboratory (the weight on which subsequent sample processing is based) will be used in calculation of the faecal radioactivity recovery.

The total recovery of radioactivity (fe_{tot} ; percent of administered radioactive dose recovered in urine and faeces overall) will be computed as the sum of the cumulative excretion in urine and faeces. If a volunteer vomits, the emesis product will be collected during the 0 to 12 hour postdose period only for potential analysis of [^{14}C] radioactivity, and if appropriate, included in calculation of the total radioactivity excreted for this volunteer.

In the case of meaningful recovery in any of the 24-hour intervals on Day 28, 35, 42 and 84, the rate of excretion (ie % administered dose/h) will be plotted against time and the area under the rate curve (AURC) for the intervals during which samples were not collected will be calculated for urine and faeces.

Determination of metabolic profiling and metabolite characterisation will be performed on relevant plasma/urine/faeces samples. The relative systemic exposure of any major metabolites will be calculated, if appropriate. This may be summarised in a separate study report.

12. STATISTICAL METHODS AND SAMPLE SIZE DETERMINATION

12.1 Description of analysis sets

12.1.1 Safety analysis set

All volunteers who received 1 dose of [^{14}C]-labelled investigational product and for whom any postdose data are available will be included in the safety population.

12.1.2 Pharmacokinetic analysis set

The PK analysis set will include all volunteers who receive 1 dose of [^{14}C]-AZD9291 and have at least 1 postdose PK measurement without important protocol deviations/violations or events thought to significantly affect the PK of the investigational product (eg, volunteer vomited at or before 2 times median t_{max} , wrong dose administered, prohibited concomitant medication, etc).

12.2 Methods of statistical analyses

Statistical analysis will be performed by using Standard Operating Procedures and Work Instructions, unless otherwise specified. Statistical analysis will be carried out by using the SAS[®] version 9.2 or higher and where appropriate, additional validated software. Other analyses than those stated below might be performed to gain information needed for the planning and analyses of future studies.

12.2.1 General principles

The analysis of data will be based on different subsets according to the purpose of analysis, ie, for safety and PK, respectively.

Given the exploratory nature, no formal statistical hypothesis testing will be performed in this study. The statistical analysis will be descriptive and consist of subject listings, graphs, and summary statistics comprising geometric mean, coefficient of variation (CV%), arithmetic mean, standard deviation (SD), median, minimum (min), and maximum (max) values as appropriate. Categorical variables (eg, gender) will be summarised in frequency tables (frequency and proportion of volunteers in the analysis set). In general, descriptive statistics will follow the rounding convention in Early Clinical Development SOPs.

Missing data will be assumed to be missing completely at random, causing a reduced sample size. Since the descriptive statistics will be presented in tables and individual data listings, no action will be taken to handle missing data.

A volunteer who withdraws prior to the last planned observation in the study period will be included in the analyses up to the time of discontinuation.

Data from nonvalid volunteers (volunteers excluded from the analysis set[s]), which are recorded in the database, will only be presented in listings.

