Each volunteer will receive 20 mg [¹⁴C]-AZD9291 oral solution (free base equivalent) containing a nominal dose of 1 µCi (0.037 MBq) activity as a single administration. Volunteers will be fasted for 10 hours prior to investigational product administration and for 4 hours after investigational product administration. Volunteers will not be allowed to consume water up to 1 hour prior to investigational product administration and for 1 hour after investigational product administration.

Comparator, dosage and mode of administration

None

Duration of treatment

Each volunteer will receive 20 mg [¹⁴C]-AZD9291 oral solution (free base equivalent) containing a nominal 1 µCi activity as a single administration.

A maximum of 28 days prior to dose administration will be allowed for the screening period (Visit 1). Each volunteer will be admitted to the study centre on Day -1 (Visit 2) and receive a single oral dose of [¹⁴C]-AZD9291 on Day 1 after a 10-hour fast. Volunteers will remain as in-patients at the study centre for 21 days after [¹⁴C]-AZD9291 administration for collection of urine and faeces, pharmacokinetic and safety assessments. Volunteers will return to the study centre for a 24-hour residency over the next 3 weeks on a weekly basis (Visit 3: Day 28 to Day 29; Visit 4: Day 35 to Day 36; and Visit 5: Day 42 to Day 43) to provide additional excreta samples as well as urine and plasma samples following discharge from the study centre.

Volunteers will return on Day 84 (Visit 6) for a final 24-hour visit which will include poststudy medical assessment. A window of ±2 days (with a minimum of 5 days between consecutive visits) may be applied for Visits 3 through 6.

The total duration of the study including screening, treatment and follow-up visits will be approximately 16 weeks. Depending on emerging data and quantification of recovery, study timings may be shortened.

Outcome variables:

Primary endpoint

- Amount and percentage of radioactive dose of [¹⁴C] radiolabelled AZD9291 recovered in urine, faeces, and in total will be calculated.

Secondary endpoints

- Amount of [¹⁴C] radioactivity in plasma and whole blood and the resulting area under the concentration-time curve from time zero to infinity (AUC), area under plasma concentration-time curve from time zero to the last quantifiable concentration (AUC_(0-t)),

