Volunteers will be resident at the study centre for 21 days following administration of the investigational product. During residency samples of blood, urine and faeces as well as safety assessments will be collected. Volunteers will be discharged on Day 21 after completion of all assessments. Volunteers will return to the study centre for a 24-hour residency on a weekly basis for a further 3 weeks (up to Day 42) for further sample collection of blood, urine, and faeces as well as safety assessments (Visit 3: Day 28 to Day 29; Visit 4: Day 35 to Day 36; and Visit 5: Day 42 to Day 43). A final 24 hour study visit will be conducted at Day 84 to Day 85 (Visit 6) which will include collection of additional blood, urine, and faecal samples as well as all final poststudy medical assessments. If at any time during return visits the subject is unable to produce a faecal sample, home collections (outpatient basis) of faeces

may be requested at the discretion of the investigator and scientific lead for individual subjects. The home collections of faeces should be brought to the study centre. Volunteers will be discharged from the study on Day 85.

A window of ± 2 days for Visits 3 through 6 can be applied, provided there is a minimum of 5 days between consecutive visits. The total duration of the study including screening, treatment and follow-up visits will be approximately 16 weeks. Depending on emerging data and quantification of recovery, study timings may be shortened.

To try and ensure a faecal sample is produced in every collection procedure lactulose will be available at the study centre and will be administered as follows:

1. If following dosing a subject does not produce a sample in a 24 hour period a single dose of 15 mL of lactulose will be given at the start of the next collection period. This will be given up to 3 times per day until samples are produced in 2 consecutive 24 hour collection periods. The lactulose will then either be discontinued or continued based on investigator judgement.
2. At admission for the return collection visits the subjects will be asked when they last opened their bowels. If this was more than 24 hours prior to the admission, lactulose 15 ml will be given. This will be given up to 3 times per day until a sample is produced. The lactulose will then either be discontinued or continued based on investigator judgement.

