5.8 Discontinuation of investigational product (Not applicable)

5.9 Withdrawal from study

Volunteers are at any time free to withdraw from the study (investigational product and assessments), without prejudice to further treatment (withdrawal of consent). These volunteers will always be asked about the reason(s) and the presence of any AEs. If possible, they will be seen and assessed by the Principal Investigator. Adverse events will be followed up (Sections [6.3.3](#) and [6.3.4](#)).

Withdrawn volunteers will not be replaced.

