The ratio of plasma AZD9291, AZ7550 and AZ5104 to plasma [¹⁴C] radioactivity concentrations (expressed as a percentage) for each sampling time will be listed by volunteer and summarised using descriptive statistics, to assess the contribution of unchanged drug to the total radioactivity in plasma over time.

A subject listing of whole blood/plasma [¹⁴C] radioactivity concentration-time ratios (expressed as a percentage) and percent distribution of radioactivity in blood cells will be presented and the data will be summarised by scheduled time using descriptive statistics.

Blood-based PK parameters will be summarised using descriptive statistics. Individual PK parameters will be presented along with descriptive statistics for all volunteers.

Urine AZD9291, AZ7550 and AZ5104 and urine [¹⁴C] radioactivity data will be summarised by scheduled collection intervals using descriptive statistics. Individual urine recovery data will be presented along with the descriptive statistics for all volunteers.

Faecal [¹⁴C] radioactivity data will be summarised using descriptive statistics. Individual faecal recovery data will be presented along with the descriptive statistics for all volunteers.

The total recovery of radioactivity over the study duration will be computed as the sum of the cumulative excretion (as % of dose) in urine, faeces, and emesis (if any). Cumulative mean recovery of radioactivity-time profiles will be graphically presented for urine, faeces, and total (sum of urine plus faeces, plus emesis, if applicable). Individual cumulative recovery data

(urine, faeces, and total) will be presented graphically and in tables along with the descriptive statistics for all volunteers.

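### The general missing-data rule does not suit the cumulative recovery endpoint: it leaves open whether a truncated total is averaged in as final recovery

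*Protocol*

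**What the plan says.** The primary endpoint in the Synopsis is the amount and percentage of radioactive dose "recovered in urine, faeces, and in total will be calculated". Section 11.2 defines total recovery, fe_tot, which "will be computed as the sum of the cumulative excretion in urine and faeces". Section 12.2.2 takes it over the whole study: "The total recovery of radioactivity over the study duration will be computed as the sum of the cumulative excretion". That section also presents individual cumulative recoveries with descriptive statistics covering all volunteers.

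The only general missing-data rule is in Section 12.2.1: "Missing data will be assumed to be missing completely at random, causing a reduced sample size", followed by the statement that "no action will be taken to handle missing data". A volunteer who withdraws early "will be included in the analyses up to the time of discontinuation". Section 12.1.2 admits a volunteer to the PK analysis set on a single postdose measurement, subject to exclusions for important deviations or events affecting PK. It does not require complete excreta collection. Section 5.9 adds: "Withdrawn volunteers will not be replaced".

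Two other provisions matter. Section 3.1 allows the schedule to change: "Depending on emerging data and quantification of recovery, study timings may be shortened". Section 11.2 has one rule for uncollected intervals. If recovery is meaningful in the late 24-hour collections (Days 28, 35, 42, 84), the area under the excretion-rate curve (AURC) is calculated for the periods without samples.

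**The concern.** A missing concentration drops out of the mean at its time point and the denominator falls by one. A cumulative total behaves differently. If one interval is missing and nothing is done, the sum can still be formed, and the missing interval contributes nothing to it. The volunteer then appears to have a final recovery when he has only a partial one.

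Assuming data are missing completely at random does not remove this. Under that assumption, dropping the volunteer leaves the expected mean unchanged. Keeping him with a partial sum does not, because the error always has the same sign.

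In a mass balance study, a shortfall of several points may be read as retained drug or an unmeasured route. With 8 volunteers and no replacement, one early case is enough to produce it. Two analysts following the same text could report different primary results from the same data.

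**Working it through.** **Structure of the sum.** From Section 6.4.1, postdose collection to 504 h comprises 14 faecal intervals (7 of 24 h, then 7 of 48 h) and 24 urine intervals (10 to 168 h, then 14 daily). The four late collections bring these to 18 and 28. A loss in any early interval carries through every later cumulative value.

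**What the text allows.** Retention of withdrawn volunteers, PK-set entry on one measurement and summaries for all volunteers together permit a truncated total to be averaged. The reference to a reduced sample size permits dropping the volunteer instead. Neither reading is excluded.

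**No figure to reproduce.** The sample size of 8 in Section 12.3 has no formula, SD or precision target.

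**Inputs for sizing the effect.**
- n = 8 (Section 12.3).
- Half-life h = 30, 50 or 110 h (Section 3.2: range 30 to 110, median 50). This is a plasma half-life, used here for excretion by assumption.
- Faecal share 80%: the rat figure in Section 1.2 is above 80%; assumed for man.
- True recovery 90%, between-volunteer SD 3, 5 or 10 points: assumed; the protocol gives neither.
- First-order excretion, F(t) = 1 − 2^(−t/h): assumed.

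**Formula.** If one volunteer of 8 keeps a truncated total, the mean falls by 90 × L / 8, where L is the fraction omitted:
- lost 24-48 h faeces: L = 0.8 × [F(48) − F(24)]
- withdrawal at time w: L = F(504) − F(w)

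| | h = 30 | h = 50 | h = 110 |
|---|---|---|---|
| F(24), F(48) | 0.426, 0.670 | 0.283, 0.486 | 0.140, 0.261 |
| F(72), F(168), F(504) | 0.811, 0.979, 1.000 | 0.631, 0.903, 0.999 | 0.365, 0.653, 0.958 |
| L, lost faeces | 0.196 | 0.162 | 0.097 |
| Fall in mean | 2.2 | 1.8 | 1.1 |
| L, withdrawal at 72 h | 0.189 | 0.368 | 0.594 |
| Fall in mean | 2.1 | 4.1 | 6.7 |
| L, withdrawal at 168 h | 0.021 | 0.097 | 0.305 |
| Fall in mean | 0.2 | 1.1 | 3.4 |

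For example, withdrawal at 72 h with h = 50: 90 × 0.368 / 8 = 4.1, so 89.9% becomes 85.8%.

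**Spread.** In simulation with SD 5 (200,000 studies per case), the average sample SD without any loss is 4.6 to 4.8. Across the three half-lives it becomes 5.5 to 7.8 (lost faeces), 7.6 to 19.4 (withdrawal at 72 h) and 4.9 to 10.7 (withdrawal at 168 h). The rise is not certain. In the mildest case (168 h, h = 30, SD 10) the SD rose in only 53% of studies. If all 8 lost the same faecal interval with h = 50, it would fall from 4.8 to 4.0.

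**If the volunteer is dropped.** The expected mean of the remaining 7 is unchanged under missing completely at random: 89.9% at h = 50 and 86.2% at h = 110.

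**The case against.** The strongest reply is that the protocol never says a missing collection counts as zero. A reader might infer that it directs this; it does not. Its wording about a reduced sample size fits dropping the volunteer from the final total, and including him until he leaves fits a contribution to earlier time points only. On that reading there is no bias under the stated assumption. This stands, and is why the point is that the text fails to settle the handling. It does not answer everything. An isolated lost sample involves no withdrawal and no point at which the volunteer leaves. Dropping withdrawn volunteers also changes who makes up the mean cumulative curve, so that curve can fall although no individual's can.

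The AURC rule in Section 11.2 is a form of rate interpolation and deserves credit. However, it is triggered only by meaningful late recovery, does not clearly cover a loss in Days 1 to 21 or an early withdrawal, and is not stated to enter fe_tot.

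Other mitigation is real. Collection is residential for 21 days, with lactulose and optional home faecal collection at return visits. A period with no stool is not missing data, since the radioactivity appears in a later stool. Individual recoveries, the median and the minimum are reported, so a truncated record would be visible. Visibility does not correct the summary mean and SD.

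Completeness cut-offs are often left to the SAP, which is not shown. Here, though, the protocol states a general rule that an SAP would have to depart from.

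**Conclusion.** The concern holds in limited form. The general rule in Section 12.2.1 is unsuitable for cumulative recovery and leaves open whether an incomplete volunteer is kept or dropped. If kept, the mean falls even under missing completely at random: for one volunteer of 8, by about 1.1 to 2.2 points for a lost 24-48 h faecal collection, 2.1 to 6.7 for withdrawal at 72 h and 0.2 to 3.4 for withdrawal at 168 h. These sizes rest on assumed 90% recovery, first-order excretion at the plasma half-life and, for the faecal case, an 80% faecal share.

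Two stronger readings are not supported. The documents do not show that recovery will be biased; that depends on an analysis choice they leave open. Nor does the spread necessarily increase. Larger falls would need a withdrawal earlier than those examined, or more than one affected volunteer.

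Possible shortening of the schedule adds to the need for a common time point, because the protocol does not say how unequal collection lengths would be combined.

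**What to change.** - Limit the no-action sentence in Section 12.2.1 to concentrations and safety data.
- Summarise fe_u, fe_f and fe_tot in volunteers with complete collection to a common time, for example 504 h, where continuous collection ends, alongside the planned total over the study duration. If timings are shortened, name the common time that replaces it.
- Define complete collection as no lost sample and no withdrawal before that time. A period without a stool counts as complete.
- List and flag incomplete volunteers, and show a sensitivity summary that includes everyone.
- Use the same volunteers at every point of the mean cumulative curve.
- State whether AURC or interpolated amounts enter fe_tot, and restrict interpolation within Days 1 to 21 to lost samples.

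The cost is wording and one extra table. The main summary may rest on 6 or 7 volunteers and still relies on the losses being unrelated to recovery; the sensitivity summary makes both visible.
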